## **SYNOPSIS**

[figure not shown]
Investigational Medicinal Product	Kit for the Preparation of Tc-99m Recombinant Human Annexin V-128 for Injection
Title of the study	A Phase I-IIa Study of safety, tolerance, pharmacokinetics, dosimetry and benefice of early nuclear medicine imaging of 99m Tc-rhAnnexin V-128 in patients with rheumatoid arthritis or ankylosing spondylitis
Study centre	Nuclear Medicine Department, CHUV, 1011 Lausanne, Switzerland
Sponsor	Advanced Accelerator Applications Switzerland S.A., [name]
Subject's Indication	Rheumatoid Arthritis (RA) or Ankylosing Spondylitis (AS)
Objectives	
Primary Objectives:
 

• To determine the safety and tolerability of imaging with 99mTc-rhAnnexin V-128.

 
Secondary Objectives:
 

• To determine the biodistribution, pharmacokinetics and radiation dosimetry of 99mTc-rhAnnexin V-128

• To demonstrate the time-dependent distribution and localization of 99mTc-rhAnnexin V-128 both in RA and AS patients

• To determine ability of early imaging with 99mTc-rhAnnexin V-128 to evaluate the presence of lesions before and after short term treatment of either RA or AS patients

Rationale	Annexin V is an endogenous human protein that binds to phosphatidylserine, a molecule expressed only on the surface of apoptotic cells. Technetium-99m (Tc-99m) is a medical isotope widely used in diagnostic imaging. 99m Tc-labelled annexin V has demonstrated the ability to image cellular apoptosis and necrosis of, among others, rheumatoid arthritis or ankylosing spondylitis conditions.
Planned number of patients	20 evaluable patients (patients who have completed Day 56 assessments) will be included in the study with either rheumatoid arthritis or with ankylosing spondylitis.  Ten enrolled patients, independently from the group (RA or AS), will take part in adosimetric and pharmacokinetics (PK) sub-study, after providing written approval.  Out of the first 6 enrolled patients, at least 3 patients must take part in the sub-study.
Study design and Methodology	This is a monocentric, open label, Phase I-IIa study  Subjects who have signed the informed consent and are eligible to participate in the study will be subjected to the following assessments: 

• At screening, patients will have a physical examination, vital signs, blood analysis (haematology, coagulation, chemistry and immunology), urine analysis, a bone scintigraphy if not already performed within 8 weeks before rhAnnexin V-128 administration, an ECG, a pregnancy test for women with childbearing potential, BASDAI, BASFI, BASMI for

[figure not shown]
	
patients with AS, DAS28 Disease Activity Score assessments for patients with RA.
 

On Day 1, patients will have whole body scintigraphies with 99mTc-rhAnnexin V-128, vital signs assessment and an ECG. A pregnancy test will also be performed prior to rhAnnexin V-128 administration. The first 3 patients (who will not take part in the sub-study) will be imaged at 60 min and at 2 hrs after administration. Next enrolled patients will be imaged at a time in line with the results of the image acquisition in the first 3 patients who will have participated in the sub-study. Additional images, blood and urine samples will be taken for the 10 patients participating in the dosimetric and PK study.

At Day 2, patients will be called over the phone to inquire if they experienced allergic reactions such as edema or rash. Patients who will participate in the PK and dosimetric sub-study will be interviewed in face to face on site meeting during the visit on Day 2. For these last patients, blood/urine analysis, whole body scintigraphy with 99mTc-rhAnnexin V-128 will be repeated 24 hours later for the dosimetric and pharmacokinetics analyses. Vital signs and ECG will also be assessed.

At Day 30+- 3 days, all patients will have immunological evaluations as well as blood (haematology and biochemistry) and urine analysis, ECG and vital signs.

At 6 weeks (Day 42) ± 2 weeks, a whole body scintigraphy with 99mTc-rhAnnexin V-128 at a time in line with the results of the image acquisition in the first 3 patients who will have participated in the sub-study, ECG, physical examination, vital signs, blood/urine analyses, a pregnancy test for women with childbearing potential, BASDAI, BASFI, BASMI for patients with AS, DAS28 Disease Activity Score assessments for patients with RA will be performed in all patients.

At Day 43, patients will be called over the phone to inquire if they experienced allergic reactions such as edema or rash.

At 8 weeks (Day 56) ± 2 weeks, vital signs and immunological evaluation will be performed.

At Day 90+- 2 weeks, all patients will have immunological evaluations, ECG, physical examination and vital signs, blood and urine analysis, BASDAI, BASFI, BASMI for patients with AS, DAS28 Disease Activity Score assessments for patients with RA.

Treatment	The single dose vial (rhAnnexin V-128: 0.40 mg) will be reconstituted with 740 MBq (20 mCi) of 99m Tc. The labelling reaction requires 90 minutes and the reconstituted radiolabelled product is stable for 6 h. For the purpose of this study, it is recommended to administer the reconstituted solution within 4 hours after completion of the labelling reaction. The drug is administered at a dose of 250 MBq as a single intravenous bolus over 10-20 seconds at Day 1 and at 6 weeks (42 days) +- 2 weeks after the first administration.
Inclusion/ exclusion criteria	
Inclusion criteria
 

Patients diagnosed with RA based on ACR/EULAR 2010 criteria with a score ≥ 6, OR Patients diagnosed with AS based on the ASAS criteria. Patients with RA must have serology assessment performed and documented at the time of enrolment.

Patient with RA active disease (DAS > 2,6) and the introduction of a Bi-DMARD treatment should be indicated. RA patients must at least be treated with DMARD (methotrexate,

[figure not shown]
	
leflunomide and sulfasalazine) or combination of these treatments for at least 3 months. Treatment will be pursued while on study.
 
OR
 
RA patients must have been previously treated with Bi-DMARD before initiation of the new Bi-DMARD treatment. The non-response of the previous Bi-DMARD treatment must be documented.
 
OR
 
Patients with ankylosing spondylitis with insufficiently controlled disease while under NSAID and indication for Bi-DMARD. These patients must be under NSAID for at least 3 months and under the same NSAID for at least 1 month prior to enrolment.
 

3. <math>\geq 18</math> years old

4. Karnofsky <math>\geq 80\%</math>

5. Negative pregnancy test for women with childbearing potential,

6. For women with childbearing potential, use of two reliable means of contraception (e.g., hormonal contraceptive, patch, vaginal ring, intrauterine device, associated with other barrier method of contraception such as the use of condoms) throughout their participation to the study

7. Absence of ECG anomaly

8. Written ICF signed

 
Exclusion criteria
 

1. Pregnancy or lactation

2. Liver impairment (ALT, AST or Bilirubin <math>> 2</math> ULN) at screening visit or baseline

3. Kidney impairment (serum creatinine <math>> 1.5</math> mg/dL)

4. History of congestive heart failure (NYHA III & IV)

5. History of malignant disease within 5 years

6. History of any disease or relevant physical or psychiatric condition or abnormal physical finding which may interfere with the study objectives at the investigator judgment

7. Known hypersensitivity to the investigational drug or any of its components

8. Participation to another clinical trial within 4 weeks before study inclusion except for patients who have participated or who are currently participating in an interventional study without any study drug administration.

Study duration and assessments: maximum 4 months (+/- 2 weeks) including the screening period
	
Dosimetry	The quantitative in vivo biodistribution of the $^{99m}$ Tc-rhAnnexin V-128 will be determined through whole-body planar imagings. In addition, a SPECT/CT will be performed on the abdominal/pelvis regions at 3 hours post administration for the first 3 patients included in the sub-study in order to generate relevant dosimetry data after extrapolation for the reconstruction with OLINDA software. Depending upon the results in those 3 patients, the SPECT/CT on the abdominal/pelvis regions will be performed at 5 hours post administration. Reconstruction will be done using iterative reconstruction incorporating CT-based attenuation correction and dual-energy-window scatter correction. Dynamic planar imaging will be acquired during the first 10 minutes followed by

[figure not shown]
Pharmacokinetics	
whole body planar images at 30min, 60 min, 2hrs, 4 hrs and 24 hrs post-injection for the first 3 patients included in the sub-study. Depending upon the results in those 3 patients, the timeframe for dosimetry measurements and PK will be confirmed or modified with a time-point at 3 hrs (instead of 2 hrs) and 6 hrs (instead of 4 hrs) for the following 7 enrolled patients in the sub-study.
 
Radiation dose to the organ of interests (particularly the kidneys), effective dose equivalent and effective dose will be calculated following the MIRD committee guidelines using the OLINDA/EXM software.
 
Blood and urine collection and counting:
 
Venous blood samples will be drawn for each subject at screening, Day 30, Day 42 and Day 90 for lab analysis (Haematology, biochemistry).
 
For patients included into the subgroup of PK and dosimetric study, blood sample will also be collected for lab analysis (Haematology, biochemistry) at Day 2. For the first 3 patients, a further 10 ml of venous blood samples will be drawn at nominal times of 0, 5, 10, 15, 30, 60 minutes as well as 2 hrs, 4hrs and 24 hrs post administration. Depending upon the results in those 3 patients, the timeframe for dosimetry measurements and PK will be confirmed or modified with a time-point at 3 hrs (instead of 2 hrs) and 6 hrs (instead of 4 hrs) for the following 7 enrolled patients in the sub-study.
 
The following whole blood and serum aliquots will be prepared as described in Appendix 2, for radioactivity measurements, and PK.
 
For immunogenicity assays, venous blood samples will be drawn for each subject at screening, at Day 30 ± 3 days, at Day 56 ± 14 days and Day 90 ± 14 days.
 
Total quantity of collected blood samples for patients (participating or not in the PK and dosimetric sub-study) is described in Appendix 3.
 
Urine sample will be collected within 24 hrs prior to 99mTc-rhAnnexin V-128 administration, preferable just prior to its administration (0 h sample) to achieve bladder emptying. Urine collections will be obtained and volume recorded, possibly in the time intervals 0-1 h, 1 h – 4 hrs, 4 hrs -16 hrs, 16 hrs – 24 hrs post administration. Dual 2 mL aliquots of urine from each period will be counted in a gamma counter at local laboratory. Urine samples (10 mL) will also be analyzed by SEC-HPLC technique at local laboratory.
 
Blood clearance fractions and effective half-life estimates from multi-term non-compartmental exponential analysis will be calculated from serial measurements of radioactivity in the whole blood and serum.
 
Pharmacokinetic analysis will be also performed based on rhAnnexin V-128 serum concentration determined by ELISA method.
 
As mentioned above, venous blood samples of 10 ml volume each will be taken from the first 3 patients at nominal times of 0, 5, 10, 15, 30, 60 minutes as well as 2 hrs, 4hrs and 24 hrs post administration. Depending upon the results in those 3 patients, the timeframe for dosimetry measurements and PK samples will be confirmed or modified with a time-point at 3 hrs (instead of 2 hrs) and 6 hrs (instead of 4 hrs) for the following 7 enrolled patients in the sub-study. The blood will be processed and aliquoted as described in Appendix 2. Two aliquots of at least 0.6 mL of serum per time-point will be frozen at -80°C.

-------------------------	--

[figure not shown]
Immunogenicity assessments	
After complete decay of radioactivity, one out of two serum samples per time-point will be shipped to the central laboratory and analyzed by ELISA to determine the rhAnnexin V-128 concentration in serum (method detailed in the Laboratory Manual).
 
Assays for anti-rhAnnexin V-128 IgG and IgM antibodies will be performed in serum samples by ELISA. For this purpose 10mL blood samples will be collected at baseline, at Day 30 ± 3 days and at Day 56 ± 14 days. An additional sample is required 3 months after the first administration of the 99mTc-rhAnnexin V-128 (Day 90 ± 14 days) in case of positive anti-Annexin antibodies outcome in previous examinations. Serum will be prepared, divided into six aliquots and frozen (-80°C) until complete decay. Three out of six serum samples per time-point will be then shipped to the centralized laboratory, where the analysis for anti-rhAnnexin V-128 antibodies will be performed (methods detailed in the Laboratory Manual).
 
24 hours after each treatment injection (at Day 2 and Day 43), each patient will be interviewed over the phone (in face to face meeting at Day 2 for patients who will participate into the PK and dosimetric sub study) in order to inquire if they experienced signs or symptoms of allergic reactions (edema, rash). If this is the case, Adverse Event(s) should be reported and recorded in the Case Report Form.

Safety and tolerability	Adverse events will be collected in the Case Report Form (CRF).

**Visit schedule – Table 1**

Study Procedures	Screening ( $\pm 4$ weeks)	Day 1	24 hours 	Day 30 $\pm 3$ days	Day 42 $\pm 2$ weeks	Day 56 $\pm 2$ weeks	Day 90 $\pm 2$ weeks
Written informed consent	X						
Inclusion/exclusion criteria	X						
Medical history	X						
Concomitant medications including RA and AS treatment	X	X	X	X	X	X	X
Disease assessment (BASDAI, BASFI, BASMI for AS for AS patients, DAS28 scales including Ultrasound assessments for RA patients)	X				X		X
Physical examination	X				X		X
Vital signs (BP and HR)	X	X	X	X	X	X	X
Lab analysis (haematology, biochemistry; urine)	X		X	X	X		X
Venous/urine sampling (PK and dosimetry) 		X 	X				
Immunogenicity by ELISA 	X			X		X	X
Urine SEC-HPLC analysis 		X	X				
Pregnancy test	X	X			X		
Standard 12-lead ECG	X	X	X	X	X		X
rh-Annexin V-128 administration 		X			X		
Bone scintigraphy 	X						
Whole Body scintigraphic imaging 		X	X		X		
Adverse Events	X	X	X	X	X	X	X

 Only for patients participating to the dosimetric and PK substudies.

 Venous blood samples of 10 ml volume each will be taken from the first 3 patients at nominal times of 0, 5, 10, 15, 30, 60 minutes and 2 hrs, 4hrs and 24 hrs post administration as described in Appendix 2 for radioactivity measurements, and PK. Depending upon the results in those 3 patients, timeframe of radioactivity measurements and PK will be confirmed or modified with a time-point at 3 hrs (instead of 2 hrs) and 6 hrs (instead of 4 hrs) as required for the following 7 enrolled patients in the sub-study. The whole blood and serum samples (bullet points 1 and 2) will be counted in an auto-gamma counting system at the CHUV/NUC laboratory.

 Anti-rhAnnexin V-128 IgG and IgM antibodies will be performed in serum samples by ELISA. For this purpose 10mL blood samples will be collected at baseline, Day 30 ( $\pm 3$  days), Day 56 ( $\pm 2$  weeks) and Day 90 ( $\pm 2$  weeks) post administration of test agent (sample at 90 days is required only in case of positive anti-annexin antibodies outcome in previous examinations). Serum will be prepared, divided into six aliquots and frozen (-80°C) until complete decay. Three out of six serum samples per time-point will be then shipped to the central laboratory.

 One urine sample will be collected within 24 hrs prior to 99mTc-rhAnnexin V-128 administration, preferable just prior to the administration of study

drug (0 h sample) to achieve bladder emptying. Quantitative urine collections will be obtained (and volume recorded) possibly in the time intervals 0-1 h, 1 h – 4 hrs, 4 hrs – 16 hrs, and 16 hrs – 24 hrs post administration. Dual 2 mL aliquots of urine from each period will be counted in a gamma counter at the CHUV/NUC laboratory.

Urine samples (10 mL aliquot) will be analysed as a function of time by SEC-HPLC technique at the local laboratory in order to gain information on the chemical status of 99mTc-rhAnnexin V-128 and on the presence of 99mTc-rhAnnexin V-128-related species.

 The first 3 patients participating to the dosimetric and PK sub-study will be imaged post administration at 30min, 60 min, 2 hrs, 4 hrs and 24 hrs after the first administration. Depending upon the results in those 3 patients, timeframes of the radioactivity measurements and PK will be confirmed or modified with a time-point at 3 hrs (instead of 2 hrs) and 6 hrs (instead of 4 hrs) as required for the following 7 enrolled patients in the sub-study. The other first 3 patients (not taking part to the sub-study) will be imaged on Day 1 at 60 min and at 2 hrs after administration. Next patients will be imaged at a time defined on the basis of the data collected in the first 3 patients participating to the dosimetric and PK sub-study. On Day 42 ± 2 weeks, all patients will be imaged at a suitable time, defined on the basis of the data collected on the first 3 patients participating to the dosimetric and PK sub-study.

24 hours after each treatment injection, each patient will be contacted to inquire if they experienced signs or symptoms of allergic reactions (edema, rash).

The bone scintigraphy must be performed at screening except for patients who already had a bone scintigraphy within 8 weeks prior to 99mTc-rhAnnexin V-128 administration. In that case, the bone scintigraphy report must be collected (after patient anonymity) and will be reviewed.

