## **Handling of Study Medication**

*99mTc-rhAnnexin V-128 must be administered at the investigational site.*

The study medication must be stored, handled and administered only by qualified/authorized personnel and must be prepared in accordance with pharmaceutical quality requirements, and radiation safety regulations.

Based on the stability tests performed (Appendix 1), the Annexin Kit can be stored upon receipt at 5°C ± 3°C at least up to 6 months..

A single dose vial containing 0.4 mg of lyophilized rhAnnexin V-128 will be reconstituted with 2 mL ± 0.2 mL containing 740 MBq ± 74 MBq (20 mCi ± 2 mCi) of 99mTc eluted from the generator. Stability studies have demonstrated radiochemical purity at 6 h from labelling greater than 90%, which is in line with current specifications of the Kit for the preparation of 99mTc-rhAnnexin V-128 for injection. The administration volume (corresponding to 250 MBq) is calculated according to the estimated time of injection, on the basis of the physical decay of the radionuclide (half-life = 6.02 h). For the purpose of this study, it is recommended to administer the reconstituted solution within 4 hours after completion of the labelling reaction.

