## **6 ASSESSMENTS**

Assessments will take place in the Nuclear Medicine Department and in the Rheumatology department CHUV, Lausanne, Switzerland.

Subjects will be evaluated for safety and tolerability in accordance with Table 1 and the following Visits Schedule:

- Voluntary written informed consent will be obtained from every subject prior to the initiation of any study-related procedures.
- Each subject's demography: gender, ethnicity, weight, height, medical history, and relevant baseline characteristics will be recorded at screening visit.
- Inclusion/exclusion criteria will be checked at Screening.
- Women of childbearing potential must have negative urine pregnancy test at screening and before each 99mTc-rhAnnexin V-128 administration.
- All patients will have a baseline DPD-99m-Tc bone scan prior to any treatment. Patients will also perform a 3 hours post injection whole body scan as described below (Imaging section). The 99mTc-DPD bone and whole body scan are not required in case the patients already performed them within 8 weeks prior to the 99mTc-rhAnnexin V-128 administration.
- Vital signs will be taken at all study visits.
- ECGs will be recorded at all study visits except for Day 56 visit to measure the different ECG intervals (RR, PR, QRS, and a more extended QT evaluation according to ICH E14, and heart rate, HR). A single ECG will be taken supine, after 5 minutes rest, and not immediately after a meal. The parameters will be measured as a mean value of minimally 3 beats. The Investigator will note in the CRF whether the ECG is normal or abnormal, as well as the clinical relevance of abnormal ECGs. Clinically relevant abnormalities will be recorded on the Adverse Event page of the CRF.
- Physical examination will be conducted at Screening, Day 42 and Day 90.

- BASDAI, BASFI, BASMI for AS, DAS28 Disease Activity Score assessments for RA will be performed at baseline, Day 42 and Day 90.
- Blood samples for haematology, coagulation, biochemistry and urinalysis will be obtained at screening, at Day 30, Day 42 and Day 90, as described in the table below. For PK subgroup of patient's blood samples will also be collected pre-injection, 24 hours post injection as described above.
- All medications taken from 2 weeks prior to the first administration date through the end of study are to be recorded as medical history and concomitant medications, included therapies for RA and AS

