## **Imaging**

Bone scintigraphy: all patients will have a baseline DPD-99mTc bone scan prior to any treatment.. Standard quality control of the camera will be performed every day before patient imaging. Patient will be injected with 9MBq/Kg of DPD-99mTc. Peak will be centered on 140KeV with a 20% windowing; a LEHR collimator will be used. It will be a triple phase bone scan including angiogram, blood pool imaging (10 minutes after injection) and 3 hours delayed imaging. Angiogram will be centered on the most symptomatic joint and/or and associated inflamed tendinous structures; acquisition will be started immediately after DPD-99mTc intravenous injection. Then 16 frames of 15 seconds will be acquired (128x128 matrix; zoom 1). Blood pool images will be acquired 10 minutes after injection and will be centered on the most symptomatic joint. A complement of imaging could be performed at this time centered on another joint. It will be images of 2 minutes (256x256 matrix, zoom 1). Delayed images will be performed 3h post injection. They will be focused on the same joints visualized on blood pool images, with the same acquisition parameters. Centered images will be completed by a whole body scan (10cm/min, 1024x256 matrix; zoom 1). SPECT images could be acquired 3h after injection centred on the most symptomatic joints (60 projections of 10 seconds, 128x128 matrix, zoom 1). On planar images, region of interest will be drawn on symptomatic joints and non symptomatic joints and ratios of activity will be measured. All patients will be subjected to early and delayed planar anterior and posterior images centered on the hands and the feet. On SPECT images, VOI will be drawn on symptomatic joints.

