The quantitative in vivo biodistribution of the 99mTc-rhAnnexin V-128 will be determined through whole-body planar imaging following the recommended procedures provided in MIRD Pamphlet No 16 [20]. Reconstruction will be done using iterative reconstruction incorporating CT-based attenuation correction and dual-energy-window scatter correction. Dynamic planar imaging will be acquired during the first 10 minutes centered on the thorax. Then whole body planar images post administration will be acquired at 30 min, 60 min, 2 hrs and 4 hrs at Day 1 and at 24 hrs post-injection for the first 3 patients of the sub-study. Depending upon the results in those 3 patients, timeframe for dosimetry measurements and PK will be confirmed or modified with a time-point at 3 hrs (instead of 2 hrs) and 6 hrs (instead of 4 hrs) for the following 7 enrolled patients in the sub-study. In addition, a SPECT/CT will be performed on the abdominal/pelvis regions at 3 hours post administration for the first 3 patients in order to generate relevant dosimetry data after extrapolation for the reconstruction with OLINDA software. Depending upon the results in those 3 patients, the SPECT/CT on the abdominal/pelvis regions will be performed at 5 hours post administration. Patient's bladder should be voided before this acquisition. A 99mTc source of known activity will be imaged before the first acquisition with the patient [33]. The activity of this source will be measured in a dose calibrator prior to imaging and used to determine the imaging system calibration factor for converting reconstructed image counts into an activity concentration. In all patients, the source regions will be the brain, lungs, heart, liver, spleen, gastrointestinal (GI) tract, kidneys and urinary bladder contents and volumes of interest (VOIs) will be drawn around these. An additional VOI will be drawn around the whole body. The salivary glands, thyroid gland and gall-bladder will be defined as 190 source regions when visible and VOIs drawn about them. The difference between the number of counts in the whole-body VOI and the sum of those in the specified VOIs will define the number of counts in the "remainder" category. In addition, a VOI will be drawn over the quadriceps femoris (to provide a measure of soft tissue uptake and washout as described below). Background will be estimated from a separate SPECT acquisition with no activity present in the field of view. We assume the VOI set about the GI tract will demonstrate a rapid and non-specific uptake by soft tissue which will clear (in parallel with observed washout from soft tissues) to be replaced by activity in the contents arising from hepatobiliary transport. In order to isolate the activity within the GI tract contents, the washout of activity from the GI tract tissues will be modelled by the measured washout of activity from the VOI set over the quadriceps femoris, rescaled to that of the gastrointestinal tract at the time of the first image acquisition, when there was no activity in the gastrointestinal tract contents, and then subtracted from the activity measured in the GI tract VOI. This procedure provides the activity due to the GI contents alone.

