6.5 Imaging assessments

To assess the suitability of 99mTc-rhAnnexin V-128 imaging for detecting RA or AS lesions before and after short term treatment by observing qualitatively the number and location of lesions at each imaging point and calculating the intensity of lesion uptake (specific) as well as quantitatively through assessment of radiotracer uptake by geometric mean of counts/ROI on anterior and posterior planar images. Only patients with available anterior and posterior planar imaging data at 1h and at 2h post-injection at both Day 1 and Day 42 assessments will be considered for this analysis.

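### The bone scan has no minimum gap before the Day 1 tracer; a gap under about 2 days would inflate Day 1 joint counts only and could look like a fall after treatment

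*Protocol*

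**What the plan says.** **Timing.** Protocol Table 1 schedules the bone scan at screening only. Footnote 7 reads: "The bone scintigraphy must be performed at screening except for patients who already had a bone scintigraphy within 8 weeks prior to" the tracer administration. Section 6 adds: "All patients will have a baseline DPD-99m-Tc bone scan prior to any treatment". The synopsis and SAP 4.8 repeat the 8-week limit. None of these places gives a shortest permitted interval.

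**Agents and acquisition.** For the bone scan, protocol section 6 (Imaging) says "Patient will be injected with 9MBq/Kg of DPD" labelled with 99mTc. The study tracer is 250 MBq, also of 99mTc. Both are acquired at 140 keV with a 20% window and a low-energy high-resolution collimator.

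**Measure.** The same Imaging section compares inflamed joints before and after treatment by target-to-background ratio (TBR) and by relative uptake, using regions fixed in size and position and read in counts. SAP 6.5 measures uptake "quantitatively through assessment of radiotracer uptake by geometric mean of counts/ROI on anterior and posterior planar images", in patients with 1 h and 2 h images at both Day 1 and Day 42.

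**Background.** The one background step is in the protocol's Dosimetry section: "Background will be estimated from a separate SPECT acquisition with no activity present in the field of view".

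**The concern.** The camera cannot tell one 99mTc agent from another in the same window. Bone-agent activity left in a joint on Day 1 is therefore counted as tracer. An acquisition with an empty field removes room and detector background, not activity inside the patient, and no image is taken before the tracer injection.

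The carry-over is one-sided. No bone scan precedes the second tracer injection, which comes at least 28 days after the first, while the new biologic starts on Day 2. Any residual raises the pre-treatment image alone, so the error points towards apparent response.

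At stake is the secondary objective of imaging lesions before and after short-term treatment. In the PK and dosimetry sub-study, the same residual would enter whole-body and organ activities that are normalised to the administered tracer activity, and the radioactivity counts in blood and urine.

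**Working it through.** The documents give no figure for the interval or the residual activity, so there is nothing to reproduce first.

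**Inputs from the protocol.**
- Bone agent: 9 MBq/kg (section 6, Imaging).
- Tracer: 250 MBq (same section).
- Half-life: section 5 calculates the injection volume "on the basis of the physical decay of the radionuclide (half-life = 6.02 h").
- Second injection: 6 weeks ± 2 weeks after the first, so at least 28 days (section 3).

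**Assumptions.**
- Weight *w* of 50 to 100 kg, central value 70 kg.
- Uptake ratio *k* of 0.5 to 10, central value 1. This is decay-corrected joint counts per injected MBq for the retained bone agent, divided by the same quantity for the tracer. Biological clearance of the bone agent lowers *k*; retention in bone near the joint raises it. The documents give no value.

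**Formulas**, for a gap of *g* hours between the two injections:
- residual *R* = 9*w* × 2^(−*g*/6.02) MBq
- contamination *c* = *k* × *R*/250
- apparent fall by Day 42 with no true change = *c*/(1 + *c*)

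Both activities decay at the same rate, so *c* is the same at 1 h and 2 h if the distributions are stable.

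**Example at 24 h, 70 kg, *k* = 1.** 630 × 0.0631 = 39.7 MBq; 39.7/250 = 15.9%; 0.159/1.159 = 13.7%.

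| Gap | Residual, 70 kg | Share of 250 MBq | Apparent fall, *k* = 1 | Fall, 50 kg and *k* = 0.5 to 100 kg and *k* = 10 |
|---|---|---|---|---|
| 24 h | 39.7 MBq | 15.9% | 13.7% | 5.4% to 69.4% |
| 36 h | 10.0 MBq | 4.0% | 3.8% | 1.4% to 36.3% |
| 48 h | 2.5 MBq | 1.0% | 1.0% | 0.4% to 12.5% |
| 72 h | 0.16 MBq | 0.06% | 0.06% | 0.02% to 0.9% |

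**Gap needed.** Solving for a contamination limit *t* gives *g* = 6.02 × log2(*k* × 9*w* / (250*t*)). For *t* = 1% this is 48 h at the central values, with a range of 39 to 71 h. For *t* = 5% it is 34 h, with a range of 25 to 57 h.

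**Day 42.** 28 days is 672/6.02 = 112 half-lives, so nothing remains.

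**TBR.** With contamination *c*J in the joint and *c*B in the background region, observed TBR = true TBR × (1 + *c*J)/(1 + *c*B). Equal contamination cancels; only the difference between the two regions biases the ratio.

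**Group level.** With ten patients in a disease group, one patient with a 24 h gap at the central values moves the mean percentage change by 13.7/10 = 1.4 points.

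**Whole body, sub-study.** If 30 to 60% of the bone agent is retained (assumption), a 24 h gap at 70 kg leaves 0.3 × 39.7 = 12 MBq to 0.6 × 39.7 = 24 MBq, or 4.8% to 9.5% of 250 MBq.

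**The case against.** The strongest reply is that a short gap is permitted but not shown to have happened. Screening spans about 4 weeks and includes laboratory tests, ECG, disease scores, ultrasound in RA and an eligibility check. Earlier scans are accepted up to 8 weeks back. Study-specific site procedures exist (protocol section 11) and may already space the two injections. This stands. A reader might infer that the Day 1 images are contaminated, or that any fall seen at Day 42 is an artefact. The documents support neither; they show only that the plan does not exclude it.

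The size depends on *k* and body weight, which are assumed. That also stands, and no single percentage should be read as the expected bias. TBR, one of the protocol's two measures, may be affected less than raw counts.

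The reach is limited too. Safety is primary. SAP 7.17 plans descriptive imaging results and an association with disease scores, SAP 7.1.1 calls all testing exploratory, and no decision rule rests on a percentage fall. PK based on ELISA measures protein, not radioactivity. Blood and urine are counted before dosing in the sub-study, and the SAP table shells report those values, so carry-over there could be seen. Those samples exist only for sub-study patients and cannot correct joint or organ image counts.

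What remains is a gap in the plan for the count-based imaging measure and image dosimetry, which is cheap to close.

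**Conclusion.** The point holds in a limited form. The plan allows a same-isotope bone scan at any time up to 8 weeks before the tracer, and it neither sets a minimum interval nor corrects image counts for residual activity. The bias matters only for gaps under about 2 days, or about 3 days at the extremes of the assumed range. At 24 h it is an apparent fall of 13.7% at the central assumptions, and about 5% to 69% across the range. At 72 h contamination is at most 0.9% in every scenario, and over most of the permitted window it is nil. The direction for raw counts is certain, because only Day 1 can be affected; for TBR it depends on the background region.

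It would be wrong to infer that the trial's main conclusion is at risk: the primary safety objective and the ELISA-based PK are not affected. This is a worthwhile correction to a secondary, descriptive analysis.

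**What to change.** **SAP, which can still act on this trial.** SAP 4.2 says recruitment was to stop by the end of September 2017, and the SAP's initial version is dated January 2018, so a scheduling rule comes too late here. In SAP 6.5, 7.14 and 7.17:
- Derive and list each patient's interval from bone-agent injection to Day 1 tracer injection. Listings of bone scintigraphy and study treatment administration are already planned.
- Use elapsed hours where times exist. Do not use the SAP 7.1.5.3 formula, which adds one day and would show a next-day tracer as 2 days. If only dates exist, a plain difference of 4 calendar days guarantees more than 72 h.
- Exclude Day 1 image data with a gap under 72 h from the before/after comparison and from image dosimetry. Repeat the analysis in all patients as a sensitivity analysis. Fix the threshold before the counts are examined.
- In the sub-study, use pre-dose blood and urine counts, decay-corrected, to detect or correct carry-over in the blood and urine radioactivity data only.

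**Protocol, for any reuse.** In Table 1 footnote 7 and section 6 (Imaging), add a lower limit to the bone-scan window, stated as a condition for valid measurement and based on the protocol's own half-life. About 12 half-lives (12 × 6.02 = 72 h) keeps contamination below 1% in all scenarios above. Record both injection times.

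**Cost.** Slightly less scheduling freedom, one derived variable, and possibly a few excluded Day 1 images in a small sample. If every gap proves long, one sentence in the report closes the matter.
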